### **5.3 Secondary Endpoints**

- Overall survival
- Progression-free survival
- Duration of response
- Adverse events, determined by NCI CTCAE v5.0

### **5.4 Exploratory Endpoints**

- Serum inflammatory cytokines
- PD-1 and PD-L1 expression in pre-treatment tumor biopsy by immunohistochemistry
- Peripheral blood may be used for future studies, such as molecular biomarker analyses

### **5.5 Estimated Accrual**

Estimated accrual for this trial is 20 subjects with hematologic malignancies over 36 months

### **5.6 Name of Funding Source**

Bristol Myers Squibb

## 6.0 SAFETY CONSIDERATIONS

### 6.1 Stopping Rules

In the event of a death on study that is deemed to be possibly, probably, or definitely attributable to the drug, further infusions will be suspended pending review by the DMC and consultation with the FDA. To further protect the safety of subjects, the study incorporates a stopping rule if the lower bound of a 1-sided 80% exact binomial confidence interval of the discontinuation rate due to medically significant Grade 3 or greater events that are possibly, probably, or definitely attributable to the drug is  $> 20\%$ . Operationally, any of the following would trigger such a rule: 2 out of the first  $\leq 6$  subjects or 3 out of the first  $\leq 9$  subjects or 4 out of the first  $\leq 13$  or 5 out of the first  $\leq 16$  or 6 out of the first  $\leq 20$  subjects have unacceptable toxicity or  $\geq$  Grade 3 AEs that are possibly, probably, or definitely attributable to drug. If the true probability of  $\geq$  Grade 3 AE is 2.5%, the probability of study suspension under the above rule is approximately 0.01; if the true probability is 40%, the probability of suspension is approximately 0.91 (probabilities estimated from 5,000 simulations).

If this rule is met, further treatment for all subjects enrolled will be immediately halted. A safety evaluation will be performed and reviewed with the FDA and DMC prior to resuming any drug.

## 7.0 SUBJECT ELIGIBILITY

### 7.1 Inclusion Criteria

1. Male and female patients
2. Diagnosis of the following tumor types
  - a. Non Hodgkin-Lymphoma, including:
    - i. Diffuse large B-cell lymphoma: Histopathologic confirmation
    - ii. Mantle cell lymphoma: Histopathologic confirmation
    - iii. Follicular lymphoma, all grades: Histopathologic confirmation
    - iv. Marginal zone lymphoma: Histopathologic confirmation
  - b. Chronic lymphocytic leukemia: Histopathologic or flow cytometric confirmation:
  - c. Multiple myeloma: Histopathologic or flow confirmation
3. Relapsed, refractory, or detectable disease after treatment with chimeric antigen receptor T-cells
  - a. Multiple Myeloma: patients must have exhausted all treatment options known to provide clinical benefit, and are refractory to a minimum of 3 prior lines of therapy (including an IMiD, PI, or anti-CD38 monoclonal antibody).
4. Have measurable disease, defined by histology:
  - a. Non-Hodgkin's Lymphoma, based on presence of lesions  $\geq 1.5$  cm that can be accurately measured in 2 dimensions by CT (preferred) or MRI, and are not included in any prior field of radiation therapy
  - b. Chronic lymphocytic leukemia: circulating lymphocytes  $\geq 5,000 / \text{mm}^3$
  - c. Multiple Myeloma, based on the International Myeloma Working Group (IMWG) criteria of having one or more of the following findings:
    - i. Serum M protein  $\geq 1.0 \text{ g/dL}$

- ii. Urine M protein  $\geq$  200 mg/24 hours
- iii. Involved serum free light chain level  $\geq$  10 mg/dL with abnormal  $\kappa/\lambda$  ratio
- iv. Measurable biopsy-proven plasmacytomas ( $\geq$  1 lesion has a single diameter  $\geq$  2 cm)
- v. Bone marrow plasma cells  $\geq$  30%
- 5. Age 18 years and older, and have the capacity to give informed consent
- 6. Anticipated survival of  $>$  3 months
- 7. ECOG performance status of 0-2 (See Appendix B)
- 8. Post CAR T cell receipt of intervening palliative radiation therapy is allowed
- 9. Adequate organ function, as defined by:
  - a. eGFR  $\geq$  20 ml/min
  - b. Alanine aminotransferase (ALT) and aspartate aminotransferase (AST)  $\leq$  3 x ULN and total bilirubin  $\leq$  2 x ULN
  - c. ANC  $\geq$  1,000/ $\mu$ L
  - d. Platelets  $\geq$  50,000/ $\mu$ L
  - e. Hemoglobin  $\geq$  8 g/dL

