## 7.2 Exclusion Criteria

- 1. Receipt of intervening systemic therapy after CAR T-cell infusion
- 2. History of another primary malignancy that has not been in remission for at least 1 year (with the exception of non-melanoma skin cancer, curatively treated localized prostate cancer, curatively treated superficial bladder cancer and cervical carcinoma in site on biopsy or a squamous intraepithelial lesion on PAP smear)
- 3. Active hepatitis B, hepatitis C at time of screening
- 4. Known (HIV) seropositivity
- 5. Subjects with uncontrolled infection
- 6. Concurrent use of other anticancer agents or experimental treatments
- 7. Active autoimmune disease requiring immunosuppressive therapy with the exception of vitiligo and autoimmune alopecia
- 8. Known active CNS involvement
- 9. Subjects with a condition requiring systemic treatment with either corticosteroids ( $>$ 10 mg daily prednisone equivalent) or other immunosuppressive medications within 14 days of study drug administration. Inhaled or topical steroids, and adrenal replacement doses are permitted in absence of active autoimmune disease
- 10. Known history of any active infectious pneumonitis
- 11. Presence of acute or chronic graft-versus-host disease (GVHD) requiring active treatment unless limited to skin involvement and managed with topical steroid therapy alone
- 12. Has active cytokine release syndrome
- 13. Pregnancy or breastfeeding: Women of childbearing potential (WOCBP) must have a negative serum or urine pregnancy test (urine pregnancy test: minimum sensitivity 25 IU/L or equivalent units of human chorionic gonadotropin [hCG]) within 14 days of the first dose of study drug.

Women must not be breastfeeding. Females of nonchildbearing potential are those who are postmenopausal greater than 1 year or who have had a bilateral tubal ligation or hysterectomy. Females of childbearing potential and males who have partners of childbearing potential must agree to use 2 effective contraceptive methods during the study and for 8months following the last dose of nivolumab.

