#### **Prohibited Concomitant Therapy During Active Study Treatment**

- The administration of concurrent medications intended to treat the primary cancer is not allowed during protocol therapy. This includes chemotherapy, investigational agent, biologic agent, or other anti-tumor agents. Radiation therapy is also prohibited
- Immunosuppressive agents (except to treat a drug-related adverse event)

- Topical and inhaled corticosteroids to treat other medical conditions are allowed. Immunosuppressive doses of corticosteroids are not permitted ( $> 10$  mg daily prednisone or equivalent), except to treat a drug-related adverse event or for treatment of adrenal insufficiency. Intermittent corticosteroid usage to treat infusion reactions is allowed

Subjects should be discouraged from taking any alternative or naturopathic medications since these agents may interact with study therapy. Any use of these medications should be at the judgment of the treating physician and documented in the subject's medical record.

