**16.0 STATISTICAL CONSIDERATIONS****16.1 Study Design**

The primary objective of the study is to determine the efficacy of nivolumab as measured by the overall response rate (ORR), in subjects with hematologic malignancies with relapsed or refractory disease after receipt of CAR T-cell therapy. ORR will be estimated, and its corresponding 95% exact binomial CI will be provided. The analyses of time-to event endpoints (DOR, PFS, and OS) will follow standard methodology by employing Kaplan-Meier and Cox proportional hazard model methodology.

Safety data will be summarized descriptively. Adverse events will be summarized by severity, seriousness, and relationship to study drug. Laboratory data will be compared to baseline values.

Additional exploratory data analyses will be conducted as appropriate.

The primary objective will be investigated by assessing if the true ORR is at least above some desirable target level following therapy with nivolumab. A subject is classified as response evaluable if they have at least one response assessment or if they discontinue from treatment due to death from any cause prior to obtaining at least one response assessment.

Based on the observations in Ansell 2018, the ORRs were low, e.g., 10% and 3% in the auto-HCT-failed and auto-HCT-ineligible, respectively. The desire is therefore to rule out a 5% ORR which will require around 25% ORR. If the sample size is 20, the study will have 85% power to detect the difference between the Null hypothesis of 5% ORR and the Alternative of 25% ORR, with a 1-sided alpha of 0.05.

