Adverse events will be recorded from the time of a subject signing consent up until 30 days after the last dose of nivolumab, or 90 days after the last dose of nivolumab in the case of serious adverse events.

For subjects with multiple myeloma only.

The Sponsor-Investigator or sub-Investigator may waive screening bone marrow aspirate and biopsy requirements. For subjects with CLL/SLL and MM, repeat bone marrow biopsy only to be done after screening to confirm CR

Pregnancy test is only required in women of childbearing potential. Verbal report of pregnancy will be reported during conduct of the trial.

Tumor assessment imaging (see section 11.1.2.5) will be performed prior to cycle 3 (within 7 days of scheduled treatment dose) and every 3 cycles thereafter. Tumor assessment labs and/or imaging will also be performed as indicated per clinical standard of care (e.g. as appropriate for disease, to evaluate clinical suspicion of disease progression). Screening PET-CT and diagnostic CT done prior to screening up to day -42 may

be used for screening assessment. PET-CT and diagnostic CT will be performed at screening, then after 2 cycles on cycle 2 day 22. Thereafter, tumor assessment will comprise diagnostic CT of chest, abdomen, pelvis every 3 months. For multiple myeloma only, PET-CT should only be done amongst subjects in whom the only measurable disease is by imaging criteria – both at screening and for follow-up.

End of treatment evaluations should be done within 30 days (+/- 14 days) of the last dose of nivolumab or prior to the start of a new anti-cancer drug, whichever is first.

Correlative studies to include peripheral blood for storage for future biomarker analyses. Please see section 15 for details on blood collection and storage.

Long-term follow-up should be done according to the subject's physician standard of care. This may be performed at subjects' local physician's offices. Long-term follow-up will assess survival and disease progression. Subjects may be contacted by the study team until death, subject withdrawal of consent, lost to follow-up, or study termination, whichever occurs first.

If available, will be tested for PD-1 and PD-L1 IHC

The use of growth factors or transfusions to meet hematologic eligibility criteria is allowed

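### Subjects need not have progressed after CAR T, and irradiated lesions can count toward response, yet no planned analysis separates these cases in the uncontrolled response rate

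*Combined protocol and SAP*

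**What the plan says.** **Disease status at entry.** Section 7.1, item 3 admits "Relapsed, refractory, or detectable disease after treatment with chimeric antigen receptor T-cells". Item 4 separately requires that subjects "Have measurable disease, defined by histology", with thresholds for lymphoma, CLL and myeloma. Neither item asks for progression after CAR T or a minimum interval since infusion. Section 7.2 excludes "Receipt of intervening systemic therapy after CAR T-cell infusion", so CAR T is always the last systemic therapy before nivolumab.

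**Radiation.** Section 7.1, item 8 states: "Post CAR T cell receipt of intervening palliative radiation therapy is allowed". No order or interval relative to the baseline scan is given. For lymphoma, the qualifying lesions must be ones that "are not included in any prior field of radiation therapy". That condition is absent from the myeloma plasmacytoma criterion (item 4.c.iv) and from target-lesion selection (Section 14.1.1). During study treatment, Section 9.2 says "Radiation therapy is also prohibited".

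**Baseline imaging.** Footnote 5 to the study calendar (Appendix A) accepts as baseline "Screening PET-CT and diagnostic CT done prior to screening up to day -42".

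**Analysis.** Section 16.1 counts a subject as response evaluable after one response assessment, or after death before any assessment. Nothing is planned by progression status, time since CAR T or radiation. Section 16.1 states the objective "in subjects with hematologic malignancies with relapsed or refractory disease after receipt of CAR T-cell therapy". Section 16.2 adds detectable disease to that population.

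**The concern.** The trial has no control arm, so every response counts for nivolumab whatever its cause. A subject with a measurable lesion that is stable or still shrinking after CAR T can enrol. If the shrinkage continues, it is scored as a nivolumab response. A lesion irradiated between the baseline scan and the first dose, or irradiated earlier and then chosen as a target, can do the same.

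The null rate does not allow for this. Section 16.1 takes it from response rates of 10% and 3% in patients defined by transplant failure or ineligibility. It is not a background rate for CAR T recipients who have not progressed. Since 4 responses in 20 are enough to reject, a small background rate matters.

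**Working it through.** **Inputs from the plan (Section 16.4).** Stop if 0 of the first 12 respond; reject if at least 4 of 20 respond; null 6%, alternative 26%. Section 16.1 gives 5% and 25% instead. The 6% null is used here because the 4-of-20 rule is stated with it.

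**Step 1: the plan's own figures.** For true response rate p,

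P(reject) = Σ (x = 1 to 12) C(12,x) pˣ (1−p)¹²⁻ˣ × P(Bin(8,p) ≥ max(0, 4−x)).

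At p = 0.26 this is 0.800, which reproduces the stated 80% power. At p = 0.06 it is 0.0286, so the stated 0.05 is the nominal level and the attained error is lower. Ignoring the futility stop, P(Bin(20, 0.06) ≥ 4) = 0.029.

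**Step 2: background responses in all subjects.** Let s be the chance that a subject who does not respond to nivolumab still meets response criteria. The documents give no value, so s is an assumption. With nivolumab at the null, the observed rate is q = 1 − (1 − 0.06)(1 − s) = 0.06 + 0.94s.

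| s | q | P(≥4/20), no interim stop | P(reject), two-stage | P(0/12) = (1−q)¹² |
|---|---|---|---|---|
| 0 | 0.060 | 0.029 | 0.029 | 0.476 |
| 2% | 0.0788 | 0.068 | 0.067 | 0.373 |
| 5% | 0.107 | 0.159 | 0.158 | 0.257 |
| 10% | 0.154 | 0.372 | 0.369 | 0.134 |

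With the 5% null, the two-stage values are 0.016, 0.045, 0.123 and 0.325.

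**Step 3: only a subset exposed.** The mechanism applies only to non-progressing or irradiated subjects. Suppose m of 20 are exposed, each with rate 0.06 + 0.94s, and the rest have 0.06 (no interim stop):

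| m | s = 10% | s = 20% | s = 30% |
|---|---|---|---|
| 2 | 0.045 | 0.063 | 0.084 |
| 5 | 0.078 | 0.152 | 0.249 |

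With m = 5, s = 10% gives 0.078 rather than the 0.372 found when all 20 are exposed. To match a 10% average with five exposed subjects, each would need 0.10 × 20 / 5 = 40%.

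**Step 4: a fixed number of background responses.** With one certain background response, P(Bin(19, 0.06) ≥ 3) = 0.10. With two, P(Bin(18, 0.06) ≥ 2) = 0.29.

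**Step 5: where radiation can enter.**
- Lymphoma: the qualifying lesion is protected at entry. Section 14.1.1 then takes up to six of the largest lesions without repeating the rule, so an irradiated lesion can contribute to the measured decrease.
- Myeloma: Appendix E asks for an M-protein or free-light-chain fall, with plasmacytoma shrinkage in addition. Radiation alone therefore cannot produce a partial response where those markers are measurable. The main exposure is disease measured only by plasmacytoma, which Section 9.4 follows by PET-CT.
- CLL: entry rests on the lymphocyte count, not on a lesion.
- All: Section 10.2 repeats blood counts, and the myeloma serum markers, on cycle 1 day 1. The 42-day allowance therefore concerns imaging only.

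**The case against.** The strongest reply is that enrolling non-progressing subjects is deliberate. Detectable disease appears in the primary objective (Sections 2.1 and 16.2), and Section 3.4 expects nivolumab to augment the response to CAR T cells. A CAR T-mediated response is then the intended effect, and weak attribution is the usual limit of a single-arm trial. This stands, and it rules out treating every response without prior progression as a failure. It does not help tell an augmented response from one that would have come anyway, and progression status is the planned screening information that bears most directly on that.

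Second, the exposed group may be small. Measurable disease is mandatory, myeloma subjects must have exhausted beneficial options, and the radiation route is narrow. The only outcome figure for CAR T non-responders is a median survival of 5.1 months (Section 3.1), which does not suggest frequent late responses. This also stands and limits the size.

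Third, an old scan can work the other way: in growing disease it understates the tumour at first dose and makes response harder to reach. That is correct, so scan age alone shows no upward bias. The gap is the missing order between scan and radiation.

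Fourth, Section 16.1 allows further exploratory analyses. A split chosen after the responses are known would carry less weight than one fixed beforehand.

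**Conclusion.** The point holds as a gap in measurement and reporting. Measurable disease without documented progression qualifies, radiation is not ordered relative to the baseline scan, the unirradiated-lesion rule stops at the lymphoma entry lesion, and the analysis does not separate these subjects.

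The size is unknown. Under assumed background rates of 2% to 10% in every subject, the chance of a positive trial at the 6% null goes from 0.029 to between 0.07 and 0.37. With five exposed subjects at 10% to 30%, it is 0.08 to 0.25. All of this rests on s, which the documents do not supply.

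Three stronger readings are tempting and not supported:
- That subjects with trace disease count toward the ORR. Item 4 of Section 7.1 requires measurable disease in everyone.
- That the true type I error is 0.37. That figure needs a 10% background rate in all 20 subjects.
- That one or two background responses decide the trial. At the null they give 0.10 and 0.29, so most such trials would still be negative.

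**What to change.** 1. **Measurement.** State that the baseline imaging used for response must post-date any radiation given after CAR T. Exclude previously irradiated lesions from target lesions in Section 14.1.1 and from plasmacytoma response measurement. This leaves the permission for radiation as it is.
2. **Analysis (Section 16.1).** Keep the primary test and the 4-of-20 rule. Prespecify ORR with exact confidence intervals separately for subjects with documented progression after CAR T and for those with measurable disease without it. Use the prior-therapy and response history already collected at screening (Section 10.1.1). Report time from CAR T infusion to cycle 1 day 1, and radiation after CAR T.
3. **Wording.** Reconcile the population in Section 16.1 with that in Section 16.2.

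Cost: small subgroups with wide intervals, to be read descriptively; an occasional screening scan that cannot be reused; and an occasional subject with plasmacytoma-only disease who needs a lesion outside the radiation field. Sample size does not change.

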#### 14.1.1 Selection of Target Lesions

Up to six of the largest dominant nodes or tumor masses selected according to each of the following:

- Clearly measurable in at least two perpendicular dimensions
- Abnormal lymph nodes are those that are either
  - >15 mm in the greatest transverse diameter (GTD) regardless of the short axis diameter, or
  - >10 mm in the short axis diameter regardless of long axis
- If possible, they should be from disparate regions of the body
- Should include mediastinal and retroperitoneal areas of disease whenever these sites are involved
- Extranodal lesions within the liver or spleen must be at least 1.0 cm in two perpendicular dimensions

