## 19.3 APPENDIX C: Lugano Classification

### Lugano Classification

| Response and Site                    | PET-CT-Based Response  | CT-Based Response   |
|--------------------------------------|--|---|
| Complete                      | Complete metabolic response

Score 1, 2, or 3* with or without a residual mass on 5PS †

It is recognized that in Waldeyer's ring or extranodal sites with high physiologic uptake or with activation within spleen or marrow (eg, with chemotherapy or myeloid colony-stimulating factors), uptake may be greater than normal mediastinum and/or liver. In this circumstance, complete metabolic response may be inferred if uptake at sites of initial involvement is no greater than surrounding normal tissue even if the tissue has high physiologic uptake | Complete radiologic response (all of the following)

Target nodes/nodal masses must regress to $\leq 1.5$ cm in LD i   |
| Lymph nodes and extralymphatic sites |  | No extralymphatic sites of disease  |
| Nonmeasured lesion                   | Not applicable   | Absent  |
| Organ enlargement                    | Not applicable   | Regress to normal   |
| New lesions                          | None   | None  |
| Bone marrow                          | No evidence of FDG-avid disease in marrow  | Normal by morphology; if indeterminate, IHC negative  |
| Partial                       | Partial metabolic response  | Partial remission (all of the following)   |
| Lymph nodes and extralymphatic sites | Score 4 or 5* with reduced uptake compared with baseline and residual mass(es) of any size

At interim, these findings suggest responding disease

At end of treatment, these findings indicate residual disease   | $\geq 50\%$ decrease in SPD of up to 6 target measurable nodes and extranodal sites

When a lesion is too small to measure on CT, assign 5 mm $\times$ 5 mm as the default value

When no longer visible, 0 $\times$ 0 mm |
|                                      |  | For a node $> 5$ mm $\times$ 5 mm, but smaller than normal, use actual measurement for calculation  |
| Nonmeasured lesions                  | Not applicable   | Absent/normal, regressed, but no increase   |
| Organ enlargement                    | Not applicable   | Spleen must have regressed by $> 50\%$ in length beyond normal  |
| New lesions                          | None   | None  |

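### The NHL size rules do not fit together at 1.5 cm: a sole node of that length is eligible, yet is either already within the CT complete-response limit or not a target node

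*Combined protocol and SAP*

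**What the plan says.** All references are to the combined protocol and SAP.

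- **Entry (7.1, item 4.a).** NHL counts as measurable on "lesions $\geq 1.5$ cm that can be accurately measured in 2 dimensions by CT (preferred) or MRI". The axis is not named, and nodal and extranodal lesions are not separated.
- **Target selection (14.1.1).** The targets are "Up to six of the largest dominant nodes or tumor masses selected according to each of the following". A node qualifies as abnormal by either of two routes. One is length, with a cut strictly above 15 mm whatever the short axis. The other is ">10 mm in the short axis diameter regardless of long axis". Liver and spleen lesions have their own minimum of 1.0 cm in two dimensions.
- **CR by CT (Appendix C).** The row opens with "Complete radiologic response (all of the following". Its nodal line reads "Target nodes/nodal masses must regress to $\leq 1.5$ cm in LD" (the LDi), and another line requires "No extralymphatic sites of disease".
- **Stable and progressive disease by CT (Appendix C).** Stable disease is a fall of less than 50% in the sum of products of diameters (SPD) without progression. The progression row treats a node as abnormal only when its LDi exceeds 1.5 cm.
- **Imaging (9.4).** NHL subjects have PET-CT plus diagnostic CT after two cycles, then diagnostic CT alone every three cycles.
- **Decision rule (16.4).** The trial stops for futility at 0 responses in 12 subjects and succeeds at 4 or more in 20.

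**The concern.** The primary endpoint is best overall response rate, so each NHL subject has to be placed clearly on one side of the response line. For that, a nodal lesion that qualifies a subject should be one on which response can be measured, and it should start outside the CR size limit. At 1.5 cm neither is guaranteed. A node can start inside the limit, so that an unchanged CT fits the stable-disease row and also the nodal size line for CR. Or it can qualify the subject without being a target node, which may leave no measured node on which a CT partial response could be shown.

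Other parts of the plan do not close the gap. No section says how to score a target node of 1.5 cm or less at baseline. No section says how the week-8 PET-CT reading combines with later CT readings to give best response. Appendix C sets no confirmation requirement, whereas Appendix E requires two consecutive assessments for myeloma.

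**Working it through.** **Inputs.** The three size rules are taken from 7.1 item 4.a, 14.1.1 and Appendix C. I assume that the 1.5 cm in item 4.a is the longest diameter and that nodes are recorded in whole millimetres.

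**Step 1: apply the rules to example nodes (LDi x short axis, mm).**

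| Node | Entry: LDi >= 15 | Target: LDi > 15 or short axis > 10 | CT CR size: LDi <= 15 |
|---|---|---|---|
| 15 x 12 | yes | yes, by short axis | yes |
| 15 x 8 | yes | no | yes |
| 14 x 11 | no | yes, by short axis | yes |
| 16 x 12 | yes | yes, by length | no |

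**Step 2: count the overlap.**
- Target and within the CR limit at baseline: LDi from 11 to 15 mm with short axis from 11 mm up to the LDi. That is 1 + 2 + 3 + 4 + 5 = 15 whole-millimetre combinations.
- Eligible, target and within the CR limit: LDi must be exactly 15 mm, which leaves 15 x 11, 15 x 12, 15 x 13, 15 x 14 and 15 x 15 mm.
- Eligible but not a target node: LDi of 15 mm with a short axis of 10 mm or less.

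**Step 3: go from node to subject.** In node-only disease the entry node is at least 15 mm and the largest nodes must be targets. The nodal size line is therefore met with no change only if the largest node is exactly 1.5 cm. Targets of 11 to 15 mm that sit beside a longer node meet the line unchanged, but the longer node must still come down to 1.5 cm. If entry rests on an extranodal lesion, CR requires that lesion to disappear.

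**Step 4: shrinkage just above the boundary.**
- One node going from 16 x 12 to 15 x 12 mm: 180/192 - 1 = -6.25% SPD, and the CR size limit is met.
- That node plus five unchanged 14 x 11 mm nodes: the SPD goes from 192 + 770 = 962 to 180 + 770 = 950, a fall of 12/962 = 1.2%. The CR size limit is again met, while a CT partial remission needs a fall of at least 50%.

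**Step 5: what one subject is worth.** One response is 1/20 = 5 percentage points, and a quarter of the four needed.
- For the two-stage rule in 16.4, P(reject) is the sum over x = 1 to 12 of P(X1 = x) P(X2 >= 4 - x), with X1 ~ Bin(12, p) and X2 ~ Bin(8, p). At p = 0.26 this is 0.800, which reproduces the stated 80% power. At p = 0.06 it is 0.029, inside the stated 0.05.
- The chance of the futility stop at 6% is 0.94^12 = 0.476.
- Suppose one of the first 12 subjects were scored a response whatever the drug did. The futility stop could not then occur. Success would need 3 or more of the other 19: 1 - (0.94^19 + 19 x 0.06 x 0.94^18 + 171 x 0.06^2 x 0.94^17) = 1 - (0.309 + 0.374 + 0.215) = 0.102.

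The 0.102 shows how sensitive the decision is to one subject. It does not estimate how often such a subject occurs.

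**The case against.** The strongest reply is that Appendix C requires target nodes to regress to the limit. A node that has not changed has not regressed, and the stable-disease row describes it well. CT CR is also composite: besides nodal size, nonmeasured lesions must be absent, organs and marrow normal, and no new lesions present. The first assessment includes PET-CT, and an avid, unchanged node would be read there as no metabolic response. A false CR would have to come later, on CT alone, in a subject already read by PET. Finally, the documents give no distribution of lesion sizes, and a largest node of exactly 1.5 cm should be uncommon.

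Most of this stands, and it limits the reach of the point. A reader might infer from the thresholds that an unchanged node scores a CR. The text does not say so. Its wording leans the other way without stating a rule for nodes that start within the limit. A reader might also infer that short-axis targets such as 14 x 11 mm generate false responders. They cannot do so alone, for the reasons in step 3 of the working.

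The reply does not answer two things. The mismatch between item 4.a and 14.1.1, which leaves an eligible 15 x 8 mm node without target status, does not depend on how CR is read. And the scoring of a baseline target of 1.5 cm or less is left to the reader of the scan.

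**Conclusion.** The inconsistency is real but narrow. At LDi = 1.5 cm, a sole node with a short axis above 10 mm is eligible, a target, and already within the CT CR size limit. A sole node with a short axis of 10 mm or less is eligible but not a target node. Short-axis targets of 11 to 15 mm LDi meet the nodal CR line unchanged but do not by themselves give a subject-level CR.

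Two stronger conclusions are not supported. One is that the error can only raise the response rate. The second case can lower it, because the subject may have no target on which to show a CT partial response. The other is that small-volume subjects are to be expected because detectable disease is eligible. Item 4 requires measurable disease separately from item 3.

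The frequency is unknown. The reason to act is that success turns on 4 responses in 20 and the correction is a matter of wording. The result assumes that item 4.a refers to the longest diameter. If both diameters had to reach 1.5 cm, the entry overlap would reduce to 15 x 15 mm and the eligible-but-not-target case would vanish. If lesions are reported to 0.1 cm, a recorded 1.5 cm covers roughly 14.5 to 15.4 mm.

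**What to change.** - In 7.1 item 4.a, require a nodal lesion to have LDi above 1.5 cm.
- In 14.1.1, require LDi above 1.5 cm for every nodal target and remove the route through the short axis alone. The alternative is to keep that route and state that a target of 1.5 cm LDi or less at baseline cannot count as CR without measured regression.
- Leave the extranodal entry size as it is. Carrying the 1.0 cm liver and spleen minimum from 14.1.1 into the entry criterion would widen eligibility.

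The strict cut is the one Appendix C already uses in its progression row. Applied to both entry and targets, it reduces the baseline overlap from 15 whole-millimetre combinations (targets) and the whole LDi = 15 mm line (entry) to none.

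The cost is wording in two sections and the loss of a rare subject whose only node is exactly 1.5 cm. The change does not remove the boundary effect in step 4 of the working: a node just above 1.5 cm can still reach the CR size limit with about 1 mm of shrinkage.
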